4.1 Treatment Dosage & Administration

4.1.1 Romidepsin

Romidepsin will be administered IV on days 1, 8, and 15 of each 28-day cycle. Initially, romidepsin will be given at a dose of 10 mg/m²; patients who tolerate 2 or more cycles (or 6 total doses) at 10mg/m^2 may be escalated to 14 mg/m² for later cycles if the following criteria are met: a) patient has not achieved a CR, and b) patient has not experienced a drug-related grade 3-4 AE. If the treatinginvestigator wishes to escalate a patient that has experienced > grade 3 treatment-related AEs, the QAM must be notified and DSMC approval granted prior to escalation. Patients who are escalated to 14 mg/m² may be de-escalated back to 10 mg/m² at the discretion of the treating investigator, but must remain at that dose for the duration of study treatment (i.e. may not be re-escalated to 14 mg/m²). All changes in dosing should be clearly documented in the patients' medical records.

On days where romidepsin is given, it does not matter whether administration occurs before or after oral lenalidomide. Infusion should occur over a span of approximately 4 hours.

Approximately 30 minutes prior to each infusion of romidepsin, it is recommended that patient be given premedication with Zofran 16 mg IVPB and dexamethasone 10 mg IVPB (or equivalent per treating investigator's discretion).

4.1.2 Lenalidomide

Lenalidomide will be given orally (PO) at a dose of 25 mg daily on days 1-21 of each 28 day cycle. NOTE: The dose and schedule should be adjusted in patients with moderate or severe renal impairment who are enrolled on the study (creatinine clearance < 60 mL/min). Please refer to Table 1b below for details. Lenalidomide should be taken at approximately the same time each day (preferably in the morning) with water. Lenalidomide capsules may be taken with or without food. Patients will be instructed to not crush, chew or open capsules. Only enough pills for 1 cycle may be dispensed at one time (prior to the start of each cycle). On days where patients will have romidepsin infusion, it does not matter whether lenalidomide is taken before or after the IV infusion.

If a dose of lenalidomide is missed, it should be taken as soon as possible on the same day. If it is missed for the entire day, it should not be made up (i.e. patients should not take 2 doses the following day). Patients will be given a mediation diary on which to record all doses taken, missed, or skipped. This diary will be reviewed with study staff during visits prior to the start of each new cycle (before medication for upcoming cycle is dispensed).

4.1.3 Treatment regimen & supportive therapies

Table 1 below summarizes the treatment regimen and recommended supportive therapies for patients on this trial.

Agent	Recommended Premedications ¹	Dose	Route	Schedule ³	Duration				
Domidencin ²	30 min prior: $5-HT3 \text{ receptor}$ antagonist4 Dexamethasone 10 10 mg/m^2 IVDays 1, 8, 1 year or 								
Romidepsin-	antagonist⁴ Dexamethasone 10 mg IVPB	14 mg/m²	IV	Days 1, 8, 15	1 year or until POD				
LenalidomideNone25 mg5poDaily Days 1-2151 year or until POD ¹ Premedication protocol is for romidepsin infusions and includes recommended agents									
¹ Premedication and trea ² The parameters pati ³ Each cycle will and with ⁴ The recommen ⁵ The dose and s severe renal imp	protocol is for romidepsin doses; similar alternate r ting investigator. s specified in the shaded ent tolerates 2 or more cy be 28 days; romidepsin ir hin +3 days of days 8 and ded agent/dose is Zofran schedule of lenalidomide s pairment, as detailed in Ta	infusions medication boxes repr ccles (6 tot nfusions sh 15. 16 mg IVF should be able 1b be	and incluc s may be resent opt al doses) nould occu PB or equi adjusted f low.	les recommend given at the dis ional dose incr at 10 mg/m ² ur within ±3 day ivalent. or patients with	ded agents scretion of the ease if rs of day 1, moderate or				

-	Table	1a:	Treatment	Regimen
---	-------	-----	-----------	---------

Table 1b: Lenalidomide Dose Adjustments for Patients with Renal Impairment

Category	Renal Function	Dose and Schedule
Moderate	Creatinine clearance 30-60 ml/min ¹	10 mg daily (Days 1-21)
Severe	Creatinine clearance < 30 ml/min	15 mg every other day (Days 1, 3, 5, 7, 9,
	(not requiring dialysis) ¹	11, 13, 15, 17, 19, and 21)

¹ Creatinine clearance (CrCl) will be measured and calculated prior to initiating each cycle as described in the Study Procedures Table in Section 5.0. (Refer to Appendix D for instructions on calculating CrCl). The dose of lenalidomide will be adjusted per Table 1b. Any questions regarding dose calculations/adjustments should be directed to the Lead Pl.

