4.2 Toxicities, Dosing Delays, and Dose Modifications

All patients receiving at least one treatment on this protocol will be evaluable for toxicity endpoints. Each patient will be assessed for the development of toxicity according to the Time and Events Table (See Section 5). Toxicity will be assessed according to the NCI-CTCAE v 4.03. Dose adjustments should be made according to the system showing the greatest degree of toxicity. Toxicity should be attributed to one study drug whenever possible. Modifications/delays may apply to only the drug which caused toxicity, or both if appropriate. If lenalidomide and/or romidepsin are dose-reduced, they may not be re-escalated (unless clinically indicated and after discussion with the PI). If study drug is delayed more than 21 days (1 treatment cycle), treatment may be discontinued after discussion with the PI.

Refer to Table 2 below for dose modification instructions. Additionally, with PI approval, dose modifications (interruptions and reductions) may be permitted for any grade AE deemed intolerable by the patient, or per treating investigator discretion (with PI approval), if thought to be in the best interest of the patient.

Please also refer to sections of this protocol that contain more detailed information on the potential adverse events and risks associated with each agent (Sections 1.2.2 and 1.3.2). Doses reduced per protocol due to occurrence of adverse events are not counted as missed doses.

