CTCAE v 4.03 Grade	Romidepsin ^{1,3} Lenalidomide ^{1,3}					
0-2	No change from original starting dose	No change from original starting dose				
3-4 (neutropenia, thrombocytopenia, and/or anemia)	Hold until ANC ≥ 1.5x10 ⁹ /L and/or platelet count ≥75x10 ⁹ /L or baseline, restart at prior dose	Hold until resolved to ≤ Grade 1, then resume at same dose				
4 (febrile (≥38.5°C) neutropenia, anemia, and/or thrombocytopenia requiring transfusion)	Hold until cytopenia returns to ≤ Grade 1 or baseline, dose reduce by 1 level ²	Hold until resolved to ≤ Grade 1, then resume at same dose				
2 nd episode of grade 3-4	Hold until ANC ≥ 1.5x10 ⁹ /L and/or platelet count ≥75x10 ⁹ /L or baseline, dose reduce by 1 level ²	Hold until resolved to ≤ Grade 1, then reduce dose by 5 mg				
3 rd episode of grade 3-4	Remove from trial	Remove from trial				
¹ Toxicity should be attributed to one study drug whenever possible. Modifications/delays may apply to only the						
drug which caused toxic	ity, or both if appropriate.					
² Romidepsin dose reductions: 1 I	² Romidepsin dose reductions: 1 level dose reduction of 14 mg/m ² to 10 mg/m ² or dose reduction of 10 mg/m ² to 8					

Table 3: Hematologic Drug-Related Toxicity Dose Delays/Reductions

mg/m². ³ Additionally, with PI approval, dose modifications (interruptions and reductions) are permitted for any grade AE deemed intolerable by the patient, or per treating investigator discretion (with PI approval), if thought to

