- ²⁰ Creatinine clearance will be measured and calculated prior to initiating each cycle (Refer to Appendix D for instructions on calculating creatinine clearance). The dose of lenalidomide will be adjusted per Table 1b. Any questions regarding dose calculations/adjustments should be directed to the Lead PI. Refer to Section 4.1.3 for additional information.

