8.2.4 Storage, Supply, and Stability

Lenalidomide is an off-white to pale-yellow solid powder. Lenalidomide is supplies as white opaque capsules imprinted "REV" on one half and "25 mg" on the other half in black ink: 25 mg bottles of 21 (NDC 59572-425-21) or 25 mg bottles of 100 (NDC 59572-425-00).

Lenalidomide should be stored away from moisture and direct sunlight and protected from excessive heat and cold. Capsules should be stored at $20^{\circ}C - 25^{\circ}C$ ($68^{\circ}F - 77^{\circ}F$); excursions permitted to $15^{\circ}C - 30^{\circ}C$ ($59^{\circ}F - 86^{\circ}F$) [See USP Controlled Room Temperature].

Care should be exercised in the handling of lenalidomide. Lenalidomide capsules should not be opened or crushed. If powder from lenalidomide contacts the skin, wash the skin immediately and thoroughly with soap and water. If lenalidomide contacts the mucous membranes, flush thoroughly with water. Procedures for the proper handling and disposal of anticancer drugs should be considered.

At the study sites, all investigational study drugs will be stored in a locked, safe area to prevent unauthorized access. Before lenalidomide is dispensed, patients must 1) have a negative pregnancy test (if applicable) and 2) be counseled about the risks associated with teratogenic agents.

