8.2.5 Protocol Dose & Administration

Lenalidomide will be administered on an out-patient basis at a dose of 25 mg daily on days 1-21 of each 28-day cycle. Lenalidomide is taken by mouth with or without food. Patients should not crush, chew or open capsules. Only a supply sufficient for 1 cycle may be dispensed at one time. Investigators may not mail lenalidomide to patients.

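### Renal dosing of lenalidomide (Table 1b) and the toxicity reductions (Tables 2 and 3, Section 4.2) have no stated order of precedence and can give opposite dose changes for a patient already on a renal dose

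*Combined protocol and SAP*

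**What the plan says.** **Renal rule.** Section 4.1.2 sets lenalidomide at 25 mg daily on days 1-21 and sends patients with clearance below 60 mL/min to Table 1b. That table gives one absolute dose per category: 10 mg daily for clearance 30-60, and for clearance below 30 "15 mg every other day (Days 1, 3, 5, 7, 9", the list running on to day 21. Footnote 1 says that clearance "will be measured and calculated prior to initiating each cycle" and adds: "The dose of lenalidomide will be adjusted per" Table 1b. Table 4 footnote 20 has the same instruction: "Creatinine clearance will be measured and calculated prior to initiating each cycle". Both footnotes send dosing questions to the Lead PI. Neither mentions an earlier toxicity reduction.

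**Toxicity rule.** For lenalidomide, Tables 2 and 3 use the step "reduce dose by 5 mg". Table 3 applies it at the second grade 3-4 hematologic episode and removes the patient at the third. Table 2 applies it at the second or third grade 3 episode, and at the first episode for certain listed events. Neither table mentions Table 1b. Section 4.2 states: "If lenalidomide and/or romidepsin are dose-reduced, they may not be re-escalated". The same sentence allows an exception where there is a clinical indication and the PI has been consulted.

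**Related text.** Section 8.2.5 gives the dose as "at a dose of 25 mg daily on days 1-21 of each 28-day cycle", and Table 4 footnote 15 also states 25 mg; neither carries a renal qualifier. Section 8.2.4 describes 25 mg capsules only.

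**The concern.** Table 1b assigns a dose by renal category, whereas Tables 2 and 3 subtract from whatever the patient is taking. Once a patient has had both kinds of change, the plan gives two answers for the next cycle and does not say which prevails. In one sequence the renal rule raises cycle exposure in a patient whose dose was cut for toxicity, at the moment renal function has worsened.

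The stake is first patient safety and then interpretation. Patients may enter with clearance as low as 30 mL/min (Section 3.1.4), which is the boundary between the two rows of Table 1b. Three sites apply the text, and two careful readers could dose the same patient differently. Toxicity that followed would enter the safety endpoint and the Section 11.11 monitoring rule as toxicity of the regimen. The documents do not allow the size of that effect to be estimated.

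**Working it through.** The plan gives no figure of its own to reproduce, so the check is dose arithmetic.

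**Formula.** mg per cycle = mg per dose × dosing days. Daily dosing on days 1-21 gives 21 doses; days 1, 3, ..., 21 give 11 doses.

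**Unreduced doses.**
- Standard (Section 4.1.2): 25 × 21 = 525 mg
- Clearance 30-60 (Table 1b): 10 × 21 = 210 mg
- Clearance below 30 (Table 1b): 15 × 11 = 165 mg

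Cycle exposure falls as renal function falls, so Table 1b is orderly taken alone. The problem arises only in combination with a toxicity reduction.

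**The conflict case: 10 mg renal dose, one reduction.**
1. 10 − 5 = 5 mg daily; 5 × 21 = 105 mg per cycle.
2. Clearance falls below 30. Table 1b gives 165 mg per cycle.
3. 165 / 105 = 1.57, a 57% rise. Each single dose goes from 5 mg to 15 mg.
4. Section 4.2 bars a rise after a reduction unless its exception is used.

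Both instructions cannot be followed for this patient.

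**A literal reading with no change of category.** If the pre-cycle adjustment is taken to restore the row's dose each time, the same patient staying at 30-60 goes back to 10 mg daily: 210 / 105 = 2.0, a 100% rise. A patient in the lower row reduced from 15 to 10 mg every other day (10 × 11 = 110 mg) goes back to 165 mg: 165 / 110 = 1.5, a 50% rise. This depends on reading the adjustment as a reset even when the category is unchanged, so it is weaker than the case above.

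**Patients starting at 25 mg.** Change in cycle exposure when Table 1b is applied after reductions:

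| 5 mg reductions | Daily dose | mg per cycle | To 30-60 row (210 mg) | To below-30 row (165 mg) |
|---|---|---|---|---|
| 1 | 20 mg | 420 | −50% | −61% |
| 2 | 15 mg | 315 | −33% | −48% |
| 3 | 10 mg | 210 | 0% | −21% |
| 4 | 5 mg | 105 | +100% | +57% |

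Four reductions are needed before cycle exposure rises. From the 10 mg renal dose, one is enough.

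**Where the steps end.** From 10 mg, two steps give 10 − 5 − 5 = 0. Table 2 can produce two steps (second and third grade 3 episodes). Table 3 alone cannot, because it gives one step and then removal. Romidepsin's reduction levels are listed in footnote 2 of Tables 2 and 3; no levels or lowest dose are listed for lenalidomide.

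**The case against.** The strongest reply is that the plan already has a safeguard. Section 4.2 names lenalidomide, has no carve-out for renal checks, and allows a rise only with a clinical indication and PI discussion. Both renal footnotes route dosing questions to the Lead PI. A reader might infer that the plan simply permits the dose to be raised; the documents do not support that. What stands against the reply is that the safeguard works only if a site notices the conflict, and the footnotes word the renal adjustment as mandatory.

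It is also fair to say that the sequence is narrow. Entry requires clearance of at least 30 mL/min, so the lower row is reached only by decline after screening. Many first grade 3-4 events lead to resumption at the same dose. For patients starting at 25 mg, Table 1b usually lowers the dose. All of this stands, and it confines the point mainly to patients already on a renal dose.

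Three further inferences should not be drawn:
- That Table 1b returns a patient to 25 mg once clearance passes 60. The table has no row above 60, and nothing instructs that return.
- That the 25 mg statements in Section 8.2.5 and Table 4 footnote 15 override renal dosing. Table 4 carries the renal rule in its own footnote 20, and Section 4.1.2 and Table 1a state it too.
- That the adjusted doses cannot be supplied. Section 8.2.4 describes only 25 mg capsules, but Section 8.2 refers to the package insert for complete information. This is a gap in description.

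**Conclusion.** The point holds as an unreconciled conflict between two stated dose rules. For a patient on the 10 mg renal dose reduced once for toxicity, a fall in clearance below 30 mL/min leads to 165 mg per cycle by one rule (+57% over 105 mg), and the other bars that rise absent its exception. This rests on reading the Table 1b footnotes as written and on no precedence statement existing elsewhere in the documents. A second gap is that nothing says what follows when the 5 mg steps are exhausted from a renal dose.

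The number of patients affected is not given. A reader might infer that movement between renal categories is expected in this population, or express each case as a share of the 20 evaluable patients. The documents give no rate of category change, and toxicity is counted in everyone who received at least one dose (Section 6.1), not in the efficacy-evaluable group. The point should be corrected because it concerns safety and costs little to resolve. It takes no position on which dose or rule is right.

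**What to change.** Reconcile Table 1b footnote 1 and Table 4 footnote 20 with Section 4.2 and Tables 2 and 3:

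1. State once, and cross-refer from each place, which rule governs when a renal adjustment and a toxicity reduction both apply.
2. State what follows when the 5 mg steps run out for a patient on a renal dose.

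The sponsor decides the doses and the order of precedence.

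As minor alignment, cross-refer Section 8.2.5 and Table 4 footnote 15 to Table 1b, and bring the capsule description in Section 8.2.4 into line with the doses named in Tables 1b, 2 and 3.

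The cost is a short protocol amendment and matching pharmacy instructions, with no added procedures or patients.

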4.2 Toxicities, Dosing Delays, and Dose Modifications

All patients receiving at least one treatment on this protocol will be evaluable for toxicity endpoints. Each patient will be assessed for the development of toxicity according to the Time and Events Table (See Section 5). Toxicity will be assessed according to the NCI-CTCAE v 4.03. Dose adjustments should be made according to the system showing the greatest degree of toxicity. Toxicity should be attributed to one study drug whenever possible. Modifications/delays may apply to only the drug which caused toxicity, or both if appropriate. If lenalidomide and/or romidepsin are dose-reduced, they may not be re-escalated (unless clinically indicated and after discussion with the PI). If study drug is delayed more than 21 days (1 treatment cycle), treatment may be discontinued after discussion with the PI.

Refer to Table 2 below for dose modification instructions. Additionally, with PI approval, dose modifications (interruptions and reductions) may be permitted for any grade AE deemed intolerable by the patient, or per treating investigator discretion (with PI approval), if thought to be in the best interest of the patient.

Please also refer to sections of this protocol that contain more detailed information on the potential adverse events and risks associated with each agent (Sections 1.2.2 and 1.3.2). Doses reduced per protocol due to occurrence of adverse events are not counted as missed doses.

CTCAE v 4.03 Grade	Romidepsin ^{1,3} Lenalidomide ^{1,3}					
0-2	No change from original starting dose	No change from original starting dose				
3-4 (neutropenia, thrombocytopenia, and/or anemia)	Hold until ANC ≥ 1.5x10 ⁹ /L and/or platelet count ≥75x10 ⁹ /L or baseline, restart at prior dose	Hold until resolved to ≤ Grade 1, then resume at same dose				
4 (febrile (≥38.5°C) neutropenia, anemia, and/or thrombocytopenia requiring transfusion)	Hold until cytopenia returns to ≤ Grade 1 or baseline, dose reduce by 1 level ²	Hold until resolved to ≤ Grade 1, then resume at same dose				
2 nd episode of grade 3-4	Hold until ANC ≥ 1.5x10 ⁹ /L and/or platelet count ≥75x10 ⁹ /L or baseline, dose reduce by 1 level ²	Hold until resolved to ≤ Grade 1, then reduce dose by 5 mg				
3 rd episode of grade 3-4	Remove from trial	Remove from trial				
¹ Toxicity should be attributed to one study drug whenever possible. Modifications/delays may apply to only the						
drug which caused toxic	ity, or both if appropriate.					
² Romidepsin dose reductions: 1 I	² Romidepsin dose reductions: 1 level dose reduction of 14 mg/m ² to 10 mg/m ² or dose reduction of 10 mg/m ² to 8					

Table 3: Hematologic Drug-Related Toxicity Dose Delays/Reductions

mg/m². ³ Additionally, with PI approval, dose modifications (interruptions and reductions) are permitted for any grade AE deemed intolerable by the patient, or per treating investigator discretion (with PI approval), if thought to

4.3 Concomitant Medications/Treatments

be in the best interest of the patient.

NOTE: No other treatment modalities or procedures are required as part of the study treatment. Any patient receiving radiation therapy and/or surgery related to progression of malignancy will be removed from protocol therapy. In addition, any patient that subsequently undergoes stem cell transplant will be removed from protocol therapy.

4.3.1 Recommended concomitant medications include:

- 5-HT3 receptor antagonist (such as Zofran 16 mg IVPB or equivalent dose) prior to romidepsin infusions
- Dexamethasone 10 mg IVPB (or similar) prior to romidepsin infusions

4.3.2 Permitted concomitant medications:

- Symptomatic treatment as needed for nausea, vomiting, and/or diarrhea, including 5-HT3 antagonists, corticosteroids, benzodiazepines, and antimotility agents
- Topical and systemic treatment for rash, including corticosteroids.
- Hormonal birth control medications.
- Concurrent antiviral therapy for HBV surface antigen positivity.
- Corticosteroids are permitted for any indication other than to treat lymphoma
- Transfusions and growth factor are permitted at physician discretion and per institutional guidelines.

4.3.3 Prohibited concomitant medications and treatments:

• Concurrent chemotherapy, radiotherapy, or other investigational agents.

NOTE: Radiotherapy is permitted to treat a single non-target lesion for symptom control.

- Corticosteroids intended to treat lymphoma (NOTE: There is no washout for prior corticosteroid treatment of lymphoma, however patients may not have received such corticosteroids for >10 days)
- CYP3A4 inducers (see appendix C) Note: As this list is constantly evolving, if a medication is incorrectly documented as prohibited in this protocol, documentation from the site pharmacist to the contrary will be acceptable for the purposes of registration.
- High risk QTc prolonging agents in the case of patients who have developed QTc prolongation on study (see appendix C)

